## EXAMINATION AND FOLLOW-UP SCHEDULE

	Before inclusion			During treatment (until progression)					After treatment
	J -21	J -14	J -7	C1 : D1, D7 and D14 C2 : D1, D7 and D14	D1 of each cycle (every 4 weeks)	D14 of each cycle	Every 8 weeks after the start of treatment	End of treatment visit	Every 8 weeks
Informed consent	X								
Clinical examination		X		X	X		X	X	X
Weight, height, BP		X		X	X		X	X	
ECOG		X			X		X	X	X
Geriatric questionnaires, quality of life		X			X		X		
Biological check-up 1 			X		X		X		
Biological check-up 2 						X		X	
Urine dipstick ± 24h proteinuria		X			X		X		
ECG		X			X 				
Thoracic and abdominal-pelvic CT	X						X		
ACE			X		X		X		
Cardiac ultrasound or myocardial scintigraphy ± cardiological opinion in case of cardiopathy 	X								
Assessment of treatment toxicity				X	X		X	X	

Biological check-up 1: CBC-PQ, natraemia, kalemia, calcemia, magnesemia, phosphoremia, uricemia, creatininemia, albuminemia, ASAT, ALAT, PAL, total and conjugated bilirubinemia, GGT, TP, TSH, lipase, INR for patients treated with AVK.

Biological check-up 2: CBC-Pq, natraemia, kalemia, creatinine, creatinine clearance, ASAT, ALAT, PAL, total and conjugated bilirubin, GGT INR for patients treated with AVK.

 For patients treated with an anti-coagulant, a coagulation test should be performed, if the values are outside the therapeutic range the dose of anticoagulant should be modified and a coagulation check should be done every week until stabilization.

 During treatment, an ECG will be done according to the investigator's choice.

 In case of heart disease, cardiac echography or myocardial scintigraphy, completed by a cardiologist's opinion if necessary, **dated less than 3 months before inclusion.**

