### 7.1 Duration of treatment

Causes of discontinuation are:

- progress
- occurrence of a second cancer
- Dose reduction of more than 2 times 40 mg
- interruption of treatment for more than 4 consecutive weeks
- patient refusal
- withdrawal of consent
- continuation of the study deleterious to the patient according to the investigator

Patients who discontinue study treatment will be managed according to local guidelines. The administration of any other anti-cancer treatment will be collected in the observation booklet at a follow-up visit.

Patients will be followed every 2 months after discontinuation of treatment, regardless of the reason for discontinuation, until death except for patients who have withdrawn their consent.

Patients who stopped treatment before progression will be followed to assess the date of first progression.

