## 8. PATIENT MONITORING

### 8.1 during treatment :

- Clinical examination: weight, height, BP, collection of toxicities and clinical tumor assessment

- Cycle 1 and 2: at D1, D7 and D14
- Cycles 3 and following: at D1 of each cycle
- At the end of treatment visit

The ECOG is completed on Day 1 of each cycle (cycle 1 and following) and at the end-of-treatment visit.

- Bioassay:

At each cycle: at D1 and D14; (for cycle 1, the biological test at D1 can be the inclusion test, if it is less than 14 days old).

The assessment at Day 1: CBC-platelets, natraemia, kalemia, calcemia, magnesemia, phosphoremia, uricemia, creatininemia, creatinine clearance, albuminemia, ASAT, ALAT, PAL, total and conjugated bilirubinemia, GGT, TP, TSH, lipase, INR for patients treated with AVK.

Assessment at D14: CBC/blood platelets, creatinine clearance, natraemia, kalemia, creatinine, ASAT, ALAT, PAL, total and conjugated bilirubin, GGT, INR for patients treated with AVK.

- At the end-of-treatment visit: CBC/blood platelet count, natraemia, kalemia, creatinine, creatinine clearance, AST, ALT, PAL, total and conjugated bilirubin, GGT

A coagulation test should be performed at D1 and D14 of each cycle, if patients are treated with anticoagulant. If the values are outside the therapeutic range, the dose of anticoagulant should be modified and a coagulation test should be performed every week until stabilization.

- Other follow-up:

During treatment, an ECG will be performed if deemed useful by the investigator.

Every 4 weeks, until progression, CEA measurement will be performed as well as quality of life and geriatric parameters assessment.

Every 8 weeks, until progression, a thoraco-abdomino-pelvic scan will be performed to evaluate the tumor response.

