## **8.2 After treatment :**

- If treatment is stopped for progression: the patient will be followed up approximately every 8 weeks to collect survival data and subsequent anti-cancer treatments.

- if the treatment is stopped for another reason: the patient will be followed every 8 weeks with a thoraco-abdomino-pelvic scanner, until progression. Then he will be followed approximately every 8 weeks to collect survival data and subsequent anti-cancer treatments.

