4.4.6 Time to autonomy deterioration

The analysis will be done if we have the questionnaire at baseline and at least one follow-up for the majority of patients.

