4.4.6.1 Definition

It is defined as the time between the date of inclusion and the date on which the IADL score decreased by at least one point from the score at inclusion. Patients alive or deceased without deterioration of autonomy will be censored at the date of last IADL assessment or the date of death.

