4.4.7.1 Definition

It is defined as the time between the date of inclusion and the date of deterioration of the Spitzer QoL Index by 2 points from the score at inclusion. Patients alive or deceased without deterioration will be censored at the date of last QoL assessment or the date of death.

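### Time to autonomy and quality-of-life deterioration: questionnaires stop at progression, so censoring the deceased at death pushes both curves up; the SAP should name the last questionnaire for everyone

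*SAP*

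**What the plan says.** SAP 4.4.6.1 defines the event as a loss of at least one IADL point and then states: "Patients alive or deceased without deterioration of autonomy will be censored at the date of last IADL assessment or the date of death". SAP 4.4.7.1 does the same for a 2-point loss on the Spitzer index: "Patients alive or deceased without deterioration will be censored at the date of last QoL assessment or the date of death". Protocol 11.1 (secondary criteria) words both rules in the same way. Both endpoints are estimated by Kaplan-Meier, with rates at 6, 9, 12 and 18 months (SAP 4.4.6.2 and 4.4.7.2).

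The assessment schedule is in protocol 8.1: "Every 4 weeks, until progression, CEA measurement will be performed as well as quality of life and geriatric parameters assessment". In the examination and follow-up schedule, the row "Geriatric questionnaires, quality of life" has no mark at the end-of-treatment visit or after treatment. For patients who stop because of progression, protocol 8.2 says that "the patient will be followed up approximately every 8 weeks to collect survival data and subsequent anti-cancer treatments". Protocol 7.1 sets the length of follow-up: "Patients will be followed every 2 months after discontinuation of treatment, regardless of the reason for discontinuation, until death".

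SAP 4.4.6 adds an availability condition, repeated in 4.4.7: "The analysis will be done if we have the questionnaire at baseline and at least one follow-up for the majority of patients".

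**The concern.** The rule names two censoring dates. The natural reading assigns the last questionnaire to the living and the date of death to the deceased. Otherwise the date of death adds nothing, because it cannot precede the last questionnaire. SAP 4.2.1 is drafted in the same way for follow-up time: last news for the living, death for the deceased.

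On that reading, a patient who progresses, has no further questionnaires and later dies counts as free of deterioration for the whole unassessed interval. Two descriptive endpoints on autonomy and quality of life would then look better than the data support, in a trial meant to describe regorafenib in elderly patients. The late rates would rest mostly on patients whom nobody is still assessing.

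**Working it through.** **Direction (no assumption about survival or deterioration needed).** At each time t_j with an observed deterioration, Kaplan-Meier multiplies by (1 − d_j/n_j). Both censoring dates give the same events at the same times, so d_j is unchanged. Moving the deceased from the last questionnaire to death can only leave n_j equal or make it larger. Every factor is then equal or larger, so the death-censored curve lies on or above the other at every time.

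**Size (illustrative).** The plan gives no figure for these endpoints, so there is none to reproduce.

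Inputs from the documents:
- 47% tumour control expected at 2 months, N = 42 (protocol 11.3, SAP 1.4).
- Questionnaires every 4 weeks (protocol 8.1).
- Scan schedule (protocol 8.1): "Every 8 weeks, until progression, a thoraco-abdomino-pelvic scan will be performed to evaluate the tumor response".
- Accrual of 2 per month, so 42/2 = 21 months. Cut-off is 12 months after the last inclusion, from the one-year minimum follow-up for overall survival.

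Assumptions, not in the documents:
- Exponential times.
- Every failure of control at 8 weeks is progression. The rate is −ln(0.47)/(56/30.4375) = 0.755/1.840 = 0.410 per month, a median of 0.693/0.410 = 1.69 months.
- Median post-progression survival of 2, 4 or 6 months.
- Median time to deterioration of 3, 6 or 12 months, independent of progression.
- Questionnaires end at the scan that documents progression, or at death.

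Each of the nine combinations was simulated with 300,000 patients. Living patients were always censored at the last questionnaire. The 6-month deterioration-free rates for the middle case and the two extremes were:

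| Post-progression / deterioration median (months) | Deceased censored at death | All at last questionnaire | True | Death − true | Death − last questionnaire |
|---|---|---|---|---|---|
| 2 / 12 | 0.802 | 0.726 | 0.706 | 0.096 | 0.076 |
| 4 / 6 | 0.675 | 0.526 | 0.499 | 0.176 | 0.149 |
| 6 / 3 | 0.475 | 0.277 | 0.249 | 0.226 | 0.198 |

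The excess over the truth is thus about 10 to 23 points, of which about 8 to 20 come from the choice of date. The remaining 2 to 3 points are visit spacing: the last questionnaire before 6 months falls at 6 × 28 = 168 days = 5.52 months, and in the middle case 2^(−5.52/6) = 0.528. At 8 weeks the excess is zero.

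**Who is still assessed.** With last-questionnaire censoring, about 1 to 3 of 42 patients are at risk at 6 months, about 1 or fewer at 9 months and 0.2 or fewer at 12 months. A check by hand, ignoring deterioration and taking 47% at 2 months as exponential, is 42 × 0.47^(t/2). It gives 4.4 unprogressed patients at 6 months, 1.4 at 9, 0.5 at 12 and 0.05 at 18. Under death-censoring, 72–89% of the 6-month risk set is no longer being assessed.

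**Availability condition.** In these scenarios 95–98% of patients have at least one follow-up questionnaire. The condition is met and the gap remains.

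**Sensitivity.**
- With 60% rather than 47% progression-free at the first scan, the middle-case excess falls from about 18 to about 14 points.
- With 1-month post-progression survival and 12-month deterioration, it is about 6 points.
- If questionnaires continued 2-monthly after progression, the difference between the two dates would be about 3 points or less.
- If the deterioration hazard doubles after progression, death-censoring is 19–27 points too high and last-questionnaire censoring is still 8–13 points too high.

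**The case against.** The strongest reply is that the wording is a loose or translated sentence, and that the sponsor may mean the last assessment for everyone. The bias then does not arise. This stands as a possibility, but nothing in either document selects that reading, and the parallel drafting in SAP 4.2.1 points the other way.

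The second reply is that assessment may not stop at progression. Protocol 11.2 calls for questionnaires at each 4-weekly evaluation without stating an end, and its falls item uses a 2-month recall at follow-up, which would suit 2-monthly visits. The empty cell in the schedule is weak evidence alone: CT is also unmarked after treatment, although protocol 8.2 requires it for patients who stopped without progression. These points lower the certainty. They do not override the explicit limit in protocol 8.1, and protocol 8.2 mentions no questionnaires at all.

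Third, the size is mostly assumption. That is correct. Protocol 11.3 also counts patients who leave before documented progression as failures, so 47% may overstate the speed of progression.

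Finally, these are untested secondary endpoints, and the planned mixed models offer another view of the same scores. Both statements are true, but the mixed models do not use the censoring rule and do not correct these curves.

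**Conclusion.** The point holds as a correction to an analysis rule. If the deceased are censored at death and questionnaires end at progression, both curves can only move up. The 10 to 23 points at 6 months are illustrative: they rest on the 47% anchor, 8-weekly documentation of progression and the assumed medians, and would be smaller with slower progression or shorter post-progression survival.

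Three stronger readings are tempting and not supported:
- A reader might infer that the documents contradict each other or leave the rule wholly undefined. The definitions in the two documents agree, and the natural reading does fix a date; the trouble is what that date does.
- A reader might infer a larger error. Stopping questionnaires at the exact, unobserved progression date gives 16 to 40 points at 6 months, but radiological progression is documented at 8-weekly scans, so that range fits the plan less well. Clinical progression between scans could move the figure somewhat towards it.
- A reader might infer that the trial's conclusion is at risk. It is not: no test or decision rule uses these endpoints, and the primary endpoint and N = 42 are untouched.

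**What to change.** Before database freeze, as SAP 1.6 requires of any adjustment, replace the censoring sentence in SAP 4.4.6.1 and 4.4.7.1 with: *Patients without deterioration, whether alive or dead, are censored on the date of their last completed IADL (respectively Spitzer) questionnaire; those with only a baseline questionnaire are censored at day 1.* Day 1 matches the convention in SAP 3.2. Show the number at risk beside each planned rate.

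This costs one sentence per definition and one line per table or figure, with no new data. Clarifying the SAP is enough for the correction. The reported rates will look less favourable, and few patients will be seen to support those from 6 months onward. Some informative censoring at progression remains, so the report should note that the estimates may still be too high if deterioration speeds up once patients progress.

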4.4.6.2 Evaluation

The time scale considered will be the month.

The time to degradation of autonomy will be plotted using the Kaplan Meier estimator and the 6, 9, 12, 18 month rates will be calculated along with their 95% confidence intervals.

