4.4.7.2 Evaluation

The time scale considered will be the month.

The time to deterioration of quality of life will be plotted using the Kaplan Meier estimator, and the 6-, 9-, 12-, and 18-month rates will be calculated along with their 95% confidence intervals.

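### Both deterioration endpoints censor deaths and report Kaplan-Meier rates, which estimate neither the incidence of deterioration nor the share of patients alive and undeteriorated

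*SAP*

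**What the plan says.** **Event.** For autonomy the event is a score drop only: "the date on which the IADL score decreased by at least one point from the score at inclusion" (SAP 4.4.6.1). For quality of life it is a 2-point fall in the Spitzer index (SAP 4.4.7.1). Death is an event in neither.

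**Censoring.** SAP 4.4.6.1: "Patients alive or deceased without deterioration of autonomy will be censored at the date of last IADL assessment or the date of death". SAP 4.4.7.1: "Patients alive or deceased without deterioration will be censored at the date of last QoL assessment or the date of death". Protocol 11.1 defines both endpoints in the same way.

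**Estimator.** SAP 4.4.6.2: "The time to degradation of autonomy will be plotted using the Kaplan Meier estimator". Rates are to be read off at months 6, 9, 12 and 18. SAP 4.4.7.2 applies the same method to the Spitzer index: "the 6-, 9-, 12-, and 18-month rates will be calculated along with their 95% confidence intervals". SAP 3.5 names only Kaplan-Meier for survival data. Neither document plans a cumulative incidence or a deterioration-free survival, and neither says whether a rate means event or event-free.

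**Data collection.** Protocol 8.1 schedules the quality-of-life and geriatric assessments every 4 weeks until progression. The protocol's examination schedule shows no questionnaire at the end-of-treatment visit or after treatment. Protocol 7.1 and 8.2 continue follow-up for survival and later treatment about every 8 weeks until death.

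**The concern.** A patient who has died can no longer lose IADL or Spitzer points. Kaplan-Meier with deaths censored treats that patient as someone who would have gone on to deteriorate at the survivors' rate, so it describes a population in which nobody dies. By contrast, SAP 4.4.5.1 counts death as an event for progression-free survival.

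Autonomy and quality of life are named secondary objectives (Protocol 2.2, SAP 1.1.2) in a study meant to describe regorafenib in elderly patients. A reader of a 12-month rate will take it either as the proportion who deteriorated by then or as the proportion still alive and well. It is neither. The gap between questionnaires ending and deaths being recorded adds a second distortion, whose direction depends on which of the two censoring dates is used.

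**Working it through.** **Plan's own figure.** The documents state no figure for these two endpoints. The trial size of 42 does reproduce (16 or more of 42: exact one-sided alpha 0.0416 at 25%, power 0.906 at 47%), but it has no bearing on this point.

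**Step 1: what holds on any data set.** At each event time with d deteriorations among r at risk:
- one minus Kaplan-Meier (1-KM) grows by KM(t-) × d/r, where KM falls only at deteriorations;
- the Aalen-Johansen incidence grows by S(t-) × d/r, where S falls at deteriorations and deaths.

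Since S is never above KM, 1-KM is never below Aalen-Johansen on the same records. For the same reason the Kaplan-Meier event-free rate is never below the event-free survival estimate. In 2,000 simulated trials of 42 patients there was no violation of the first inequality under either censoring date.

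**Step 2: size if assessment continued until death.** All inputs here are assumptions. Take constant hazards, median deterioration 8 months and median overall survival (OS) 6 months, so a = ln2/8 = 0.0866 and b = ln2/6 = 0.1155 per month.
- 1-KM = 1 - exp(-a t)
- cumulative incidence = a/(a+b) × (1 - exp(-(a+b)t)), with a/(a+b) = 0.4286
- alive and undeteriorated = exp(-(a+b)t)

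At 12 months: 1-KM = 1 - exp(-1.040) = 64.6%. Incidence = 0.4286 × (1 - 0.088) = 39.1%. Alive and undeteriorated = 8.8%.

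| Month | 1-KM % | Incidence % | KM event-free % | Alive and undeteriorated % |
|---|---|---|---|---|
| 6 | 40.5 | 30.1 | 59.5 | 29.7 |
| 9 | 54.1 | 35.9 | 45.9 | 16.2 |
| 12 | 64.6 | 39.1 | 35.4 | 8.8 |
| 18 | 79.0 | 41.7 | 21.0 | 2.6 |

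Now let median OS run from 4 to 10 months and median deterioration from 4 to 12.
- At 6 months the excess of 1-KM over incidence runs from 5 points (deterioration 12, OS 10: 29.3 against 24.2) to 21 (4 and 4: 64.6 against 43.8).
- At 18 months the four corners of the range give 24 (12 and 10: 64.6 against 40.8) to 46 (4 and 4: 95.6 against 49.9).
- The largest 18-month gap lies inside the range. At deterioration 5.5 and OS 4, 1-KM = 1 - 2^(-18/5.5) = 89.7%, incidence = 0.421 × (1 - 0.005) = 41.9%, and the gap is 48 points.

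**Step 3: the protocol's schedule.** The Step 2 gaps do not carry over directly, because questionnaires end at progression. A simulation with 4-weekly assessments stopping at progression used assumed medians of 2.5 months to progression, 7.6 OS and 8 deterioration. It gave:

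| Month | True deterioration before death % | 1-KM, censored at last assessment % | 1-KM, deaths censored at death % | Aalen-Johansen, all deaths counted at death % |
|---|---|---|---|---|
| 6 | 33.8 | 37.9 | 25.8 | 21.8 |
| 9 | 40.8 | 50.9 | 29.8 | 23.7 |
| 12 | 44.5 | 64.1 | 32.4 | 24.5 |
| 18 | 47.5 | 77.7 | 34.5 | 24.7 |

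Censoring at death counts the unassessed months as time at risk without an event, and the rate falls below the truth. Censoring at the last assessment overstates here. If the deterioration hazard is four times higher after progression, last-assessment censoring understates at 6 months (46.7% against 56.5%) and overstates by 12 (74.2% against 69.7%). In every scenario run, the Kaplan-Meier event-free rate exceeded the share alive and undeteriorated. At 12 months in the table's scenario that share is 10.3%, against 35.9% or 67.6% by censoring date.

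**The case against.** The SAP never claims that these rates are the share alive and undeteriorated. They are labelled as time-to-deterioration rates with a stated censoring rule, which can be read as a cause-specific description, and mortality is reported separately through overall and progression-free survival. The endpoints carry no hypothesis or decision rule. They are analysed only if most patients have a baseline and a follow-up questionnaire (SAP 4.4.6, 4.4.7). All of this stands, and it limits the severity. It does not tell the reader what the 6- to 18-month figures are proportions of.

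A reader might infer that the rates overstate how many patients deteriorate whichever censoring date is used. The documents do not support that. Protocol 8.1 ends the questionnaires at progression while Protocol 8.2 follows deaths afterwards, so censoring at death can understate true deterioration (Step 3). The overstatement is certain only against the cumulative incidence on the same records. Nor do the documents show that most patients die within 18 months: the 3-month life expectancy in Protocol 3.1 is an eligibility minimum, and no survival figure is given.

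It can also be said that switching to Aalen-Johansen alone could make matters worse. That is correct. With every later death counted as competing, patients who deteriorate unseen after progression and then die are counted as dying undeteriorated (24.5% against a true 44.5% at 12 months in Step 3). The change therefore needs a rule for the unassessed interval.

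**Conclusion.** The point holds in this form: for both endpoints the planned Kaplan-Meier rates estimate neither the incidence of deterioration nor the proportion alive and undeteriorated, and no other planned analysis supplies either quantity. That 1-KM is at least the cumulative incidence on the same records follows from the estimators and needs no assumption. The size does need assumptions. The 5 to 21 points at 6 months and 24 to 48 at 18 months rest on constant hazards, assessment until death and the assumed ranges of medians, and are illustrative only. Against true deterioration the direction is open: censoring at death can understate it, and censoring at the last assessment will usually overstate it, though not at early time points if decline accelerates after progression. Severity is minor to moderate: two named secondary objectives are affected, both descriptive, and the primary decision is untouched.

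**What to change.** In SAP 4.4.6 and 4.4.7:

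1. Report the Aalen-Johansen cumulative incidence of deterioration with death as the competing event, and beside it deterioration-free survival (deterioration or death), each with 95% confidence intervals. Keep Kaplan-Meier only as a cause-specific supplement.
2. Replace the two alternative censoring dates by one rule. Censor at the last questionnaire those patients whose assessments have stopped. Count a death as a competing event (or as an event, for deterioration-free survival) when it falls within a stated window after the last questionnaire, for example two 4-week assessment intervals. Add a sensitivity analysis counting all deaths.
3. State whether a rate means event or event-free, and that the results describe deterioration while under assessment. The rule cannot recover deterioration that occurs after questionnaires end.

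Protocol 11.1 carries the same censoring sentences and should be aligned or cross-referenced. The cost is SAP wording and a little more analysis in the SAS version already named, with no new data. SAP 1.6 allows changes before the database is frozen, where unforeseen issues require statistical adaptation. The downside is fewer patients at risk at the late time points.
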